**Table 16: Intra-Scanner Results Across 3 Reading Pathologists for Each Scanner and Overall**

	Number of Pairwise Agreements	Number of Comparison Pairs	Agreement Rate %
Scanner A	a 	1134	(a  )/1134
Scanner B	a 	1134	(a  )/1134
Scanner C	a 	1134	(a  )/1134
Overall	a*	3402	(a*)/3402

To preserve the correlation structure of multiple readings of the same feature on an FOV, the bootstrap method will be used to derive a two-sided 95% confidence interval (CI) for the percent positive agreement. An FOV will be the bootstrap re-sampling unit.

The strategy in bootstrapping is to approximate the data generating mechanism (the data distribution function) using an empirical estimate. By design, the 378 study features are divided into 3 sets of 126 FOVs and each set is randomly assigned to a Scanner. Then 3 repeated scans (iterations) for each FOV and within each scanner are created for evaluation by each Reader. Since sets of FOVs are nested within scanners in this study, for bootstrap resampling the 3 scanners will be chosen **without** replacement (i.e., the same scanner cannot be sampled more than once).

After all data are collected, the database is cleaned and locked, the following data generation mechanism will be followed to preserve the correlation structure in this sub-study.

- a. Choose 3 scanners **without** replacement (because each reader should read 378 FOVs (126 FOVs per scanner)
- b. For each scanner, choose 126 FOVs **with** replacement from each set assigned to that scanner.
- c. Identify the reader for each of the selected FOV-scanner combinations.
- d. For each FOV-scanner-reader combination, calculate the within RP agreement status between reading sessions (1, 2), (1, 3), and (2, 3).
- e. Estimate overall intra-scanner percent positive agreement using the sampled data.
- f. Repeat step a to step e at least 1000 times to estimate a two-sided 95% confidence interval for the percent positive agreement.

Note: when the estimated agreement rate is at extreme values such as 0% or 100%, the arcsine variance transformation approach, using the Anscombe correction for the continuity will be used to calculate the 95% confidence interval instead of using the bootstrap.

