#### **6.4.3 Secondary Features**

The objective of this analysis is to investigate the repeatability/reproducibility of the readers' absence or presence calls of the secondary features. For a given magnification, each of the 7 features will be considered primary for 18 study FOVs (3 organs x 6 FOVs per organ) and will be considered secondary for the remaining 108 (6 primary features with the same magnification x 3 organs x 6 FOVs per organ) study FOVs.

It is possible that a given feature may be absent from the majority of the 108 study FOVs. Sham features are not considered.

The secondary features analysis will be based on the repeatability/reproducibility for each secondary feature separately. To perform the secondary analysis for a specific feature, say feature X, 3 scans (Iteration 1, Iteration 2, and Iteration 3) per scanner will be used. In the 3 scans from Set 1 on Scanner A, there are 6 FOVs primary for feature X among 42 FOVs and 36 FOVs secondary for feature X. Thus, 36 FOVs will be used to construct a 2x2 table for whether the secondary feature was observed.

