**Table 19: Overall Secondary Feature Agreement Rate**

		Secondary Feature is Observed Using Iteration j		
		Yes	No	
Secondary Feature is Observed Using Iteration i	Yes	a *	b *	a * +b *
	No	c *	d *	c * +d *
		a * +c *	b * +d *	972

This overall contingency table (Table 19) will be generated for each of the 21 study features (7 features per magnification, 3 magnifications) that appear as a secondary feature and the positive, negative, and overall agreement rates for each secondary feature will be estimated as:

positive agreement	$a^*/972$
negative agreement	$d^*/972$
overall agreement	$(a^*+d^*)/972$

To preserve the correlation structure of multiple readings of the same secondary feature on an FOV, the bootstrap method will be used to derive a two-sided 95% confidence interval (CI) for the overall percent positive agreement. The following data generation mechanism will be followed to preserve the correlation structure in this sub-study.

- Choose 3 scanners **without** replacement.
- For each scanner, choose 36 FOVs **with** replacement from each set assigned to that scanner.
- Identify the reader for each of the selected FOV-scanner combinations.
- For each FOV-scanner-reader combination, calculate the within RP agreement status between reading sessions (1, 2), (1, 3), and (2, 3).
- Estimate the overall intra-scanner percent positive agreement using the sampled data.
- Repeat step a to step e at least 1000 times to estimate a two-sided 95% CI for the percent positive agreement.

Two-sided 95% CI for the negative and overall agreement rates will be estimated concurrently using the same bootstrap. When the estimated agreement rate is at extreme values such as 0% or 100%, the arcsine variance transformation approach, using the Anscombe correction for the continuity, will be used to calculate the 95% confidence interval instead of using the bootstrap.

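### At 0% or 100% the SAP's arcsine fallback has no adjustment for FOV clustering and no stated n; with pairs as n, limits can sit up to about nine times too close to the boundary (about three for inter-site)

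*SAP*

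**What the plan says.** For primary features, SAP 6.4.1 states "An FOV will be the bootstrap re-sampling unit", so that the correlation between repeated readings of an FOV is kept. A note after the bootstrap steps adds that "when the estimated agreement rate is at extreme values such as 0% or 100%, the arcsine variance transformation approach", with the Anscombe correction, is used instead of the bootstrap. The source cited there compares interval estimators for a single binomial proportion.

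For secondary features, SAP 6.4.3 gives the same reason: "To preserve the correlation structure of multiple readings of the same secondary feature on an FOV, the bootstrap method will be used". It adds "Two-sided 95% CI for the negative and overall agreement rates will be estimated concurrently using the same bootstrap", and then repeats the switch: at extreme values the "arcsine variance transformation approach, using the Anscombe correction for the continuity, will be used to calculate the 95% confidence interval". The rates are defined as a*/972, d*/972 and (a*+d*)/972.

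SAP 6.5.3 applies the 6.4.3 method to the inter-scanner sub-study. SAP 6.6.3 applies a similar method to the inter-site sub-study, with 324 comparisons per feature. None of these sections says what n enters the arcsine formula.

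On sparsity, SAP 6.4.3 says "It is possible that a given feature may be absent from the majority of the 108 study FOVs". Protocol 8.1.3 also expects few secondary features per FOV.

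**The concern.** The bootstrap is there to respect clustering. The fallback that replaces it assumes independent trials, and a programmer who looks for n will find only pair counts. Nine pairs from one FOV are not nine independent pieces of evidence, so entering 972 can claim far more certainty than 108 FOVs can give.

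The boundary is a plausible outcome. If readers never call a secondary feature, then a* = 0, d* = 972 and overall agreement is 100%, so all three intervals for that feature switch to the fallback together. There are 21 features and three sub-studies. At stake is the stated precision of descriptive results that the SAP plans to report in a study meant to support a 510(k) submission.

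**Working it through.** **1. Reproduce the SAP's counts.** A feature "will be considered secondary for the remaining 108 (6 primary features with the same magnification x 3 organs x 6 FOVs per organ"), that is 6 × 3 × 6 = 108 FOVs. Intra- and inter-scanner: 108 FOVs × 3 readers × 3 pairings = 972, as in SAP Table 19. Inter-site: 108 × 3 = 324, as in SAP 6.6.3. Primary overall: 378 × 9 = 3402. All match. Pairs per FOV (m) are therefore 972/108 = 9 and 324/108 = 3.

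**2. Arcsine limit at a count of zero.** Assumed form (the SAP cites the method but prints no formula):

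upper limit = sin²( asin√[(3/8)/(n + 3/4)] + 1.96/(2√(n + 1/2)) ), mirrored at 100%.

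- n = 972: asin term 0.01964, plus 0.03143, gives sin²(0.05106) = 0.260%.
- n = 108: 0.05876 + 0.09408 gives sin²(0.15284) = 2.318%.
- Ratio 8.90. At 100% the lower limits are 99.740% and 97.682%.
- Inter-site, n = 324 against 108: 0.779% against 2.318%, ratio 2.97.

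The ratio barely depends on the form. With an added continuity term of 1/2, the limits for 972 and 108 are 0.377% and 3.344% (8.88). Clopper-Pearson gives 0.379% and 3.358% (8.86).

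**3. Dependence on the within-FOV correlation ρ.** The documents give no ρ. Put n_eff = mF/(1 + (m − 1)ρ), with F = 108, into the formula of step 2. The factor is the limit divided by the limit with pairs as n.

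| ρ | m = 9: n_eff, limit, factor | m = 3: n_eff, limit, factor |
|---|---|---|
| 0 | 972, 0.260%, 1.0 | 324, 0.779%, 1.0 |
| 0.1 | 540, 0.468%, 1.8 | 270, 0.934%, 1.2 |
| 0.25 | 324, 0.779%, 3.0 | 216, 1.166%, 1.5 |
| 0.5 | 194, 1.295%, 5.0 | 162, 1.552%, 2.0 |
| 0.75 | 139, 1.808%, 6.9 | 130, 1.936%, 2.5 |
| 1 | 108, 2.318%, 8.9 | 108, 2.318%, 3.0 |

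An exact beta-binomial limit for zero events gives lower intermediate factors for m = 9 (1.4, 2.0, 3.2 and 5.1 at ρ = 0.1, 0.25, 0.5 and 0.75) and the same end point.

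**4. Overall agreement at 100%: independence is impossible.** Three yes/no reads give three pairs. If all reads agree, no pair is discordant; otherwise exactly two are. One or three discordant pairs cannot occur. Even if the three readers were fully independent, the units would be 108 × 3 = 324 triples, and the limit would lie 0.779% × 2/3 = 0.52% from 100%. Using 972 pairs gives 0.26%, a factor of 2.0. If readers move together, 2.318% × 2/3 = 1.55%, a factor of 5.9. For inter-site the factor is 1.55/0.779 = 2.0. So for overall agreement the pair-based limit is too tight by 2.0 to 5.9 (inter-site 2.0), whatever ρ is.

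**5. Acceptance criterion.** With primary intra-scanner positive agreement at 100%, the lower limit is 99.925% (n = 3402) or 99.332% (n = 378). Both exceed 85%.

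**6. Per-scanner rates.** SAP 6.4.3 counts, for one set on one scanner, "there are 6 FOVs primary for feature X among 42 FOVs and 36 FOVs secondary for feature X". SAP Table 6 sends all three sets to each scanner, through different readers. The 324 pairs in Table 18 therefore rest on 3 × 36 = 108 distinct FOVs with three pairs each, and the 1134 primary pairs per scanner rest on 3 × 126 = 378.

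**The case against.** The strongest reply is that the SAP never tells anyone to use pairs as n. The counts 972 and 324 are denominators of point estimates, not declared sample sizes. That stands: the use of pairs is an inference, though the natural one, and the text does not support saying that the SAP prescribes a wrong n.

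A reader might also infer that leaving the bootstrap is itself the error. It is not. When every result is identical, resampling FOVs returns a zero-width interval, so something must replace it.

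A third reading is that the limits will be nine times too tight. That is the ceiling, reached only when all nine pairs on an FOV move together. For positive agreement at 0% the documents are compatible with any factor from 1 to about 9.

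Nor do the documents show that the fallback will be used. Sparse is not zero, and a* = 0 needs no concordant positive pair at all. It would also be wrong to expect primary negative agreement of 0% because every FOV contains its primary feature: d counts pairs in which the feature was missed twice, which presence does not prevent.

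Scope is limited too. The note stands only in 6.4.1 and 6.4.3. The cross-references in 6.5.3 and 6.6.3 cover secondary features; 6.5.1 and 6.6.1 contain no such note.

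These replies narrow the point without removing it. Step 4 shows that for overall agreement no correlation makes the pairs independent, so leaving n open is more than a missing detail.

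**Conclusion.** The point holds in a limited form. At 0% or 100% the SAP moves from a method that respects FOV clustering to one that does not, and leaves n unstated. If the printed pair counts are used:

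- **Secondary features, intra- and inter-scanner:** limits are too close to the boundary by a factor of up to about 9 (0.26% against 2.32% at 0%; 0.38% against 3.34% with a continuity term).
- **Secondary features, inter-site:** up to about 3 (0.78% against 2.32%).
- **Overall agreement at 100%:** at least about 2 in every sub-study.

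These sizes assume pairs as n and an arcsine form that the SAP does not print; the ratios are stable across the forms tried. Where a factor falls below its ceiling depends on a correlation that the documents do not give and that cannot be estimated when all results are identical.

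The conclusion should not be stretched to the study's decision. The 85% criterion applies to primary positive agreement and is met at 100% under either n. Secondary features carry no acceptance criterion. The effect is on descriptive intervals.

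**What to change.** Amend the note in SAP 6.4.1 and 6.4.3, so that it carries through 6.5.3 and 6.6.3:

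- Keep a fallback, but replace the open-ended trigger, which names 0% and 100% only as examples, with a count of exactly 0 or equal to the denominator. Use the bootstrap in all other cases.
- Set n to the number of distinct FOVs behind the rate: 378 for primary features and 108 per secondary feature. For any per-scanner interval use 126 and 36 if the rate rests on one set on that scanner; pooled over the three readers it rests on 378 and 108.
- Describe this n as a conservative choice, because the within-FOV correlation cannot be estimated at the boundary.
- Print the arcsine formula, including whether a continuity term is added.

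The cost is a few lines of text and some wider secondary intervals. There is one awkward consequence. With a single positive pair, the FOV is drawn Binomial(36, 1/36) within its set, with 97.5th percentile 3. A percentile bootstrap would then give an upper limit of about 3/972 = 0.31%, below the 2.32% at exactly zero. The SAP should acknowledge that the limit at zero may exceed the bootstrap limit when there are only one or two positive pairs.

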#### **6.4.2 Overall Agreement and Negative Agreement**

In addition to percent positive agreement, percent negative agreement and the overall agreement rate will be estimated with their corresponding two-sided 95% confidence intervals.

From Table 15, which is all pairwise comparisons within Scanner A across all 3 reading pathologists, the overall agreement rate can be estimated as  $(a^i + d^i)/1134$ , and the percent negative agreement can be estimated as  $d^i/1134$ , for  $i = 1$  to 3 corresponding to Scanner A, Scanner B and Scanner C. The results can be summed across all 3 readers to obtain the respective overall estimates.

Two-sided 95% confidence intervals for the percent negative agreement and the overall agreement rate will be estimated using bootstrapping. The rates will be estimated concurrently with positive agreement; no separate bootstrapping will be performed.

#### **6.4.3 Secondary Features**

The objective of this analysis is to investigate the repeatability/reproducibility of the readers' absence or presence calls of the secondary features. For a given magnification, each of the 7 features will be considered primary for 18 study FOVs (3 organs x 6 FOVs per organ) and will be considered secondary for the remaining 108 (6 primary features with the same magnification x 3 organs x 6 FOVs per organ) study FOVs.

It is possible that a given feature may be absent from the majority of the 108 study FOVs. Sham features are not considered.

The secondary features analysis will be based on the repeatability/reproducibility for each secondary feature separately. To perform the secondary analysis for a specific feature, say feature X, 3 scans (Iteration 1, Iteration 2, and Iteration 3) per scanner will be used. In the 3 scans from Set 1 on Scanner A, there are 6 FOVs primary for feature X among 42 FOVs and 36 FOVs secondary for feature X. Thus, 36 FOVs will be used to construct a 2x2 table for whether the secondary feature was observed.

**Table 17: Secondary Feature Agreement Rate for Scanner A**

		Secondary Feature X is Observed Using Iteration 2		
		Yes	No	
Secondary Feature X is Observed Using Iteration 1	Yes	a	b	a+b
	No	c	d	c+d
		a+c	b+d	36

As for overall positive agreement for the primary feature (see Table 15), nine (9) 2x2 tables will be pooled within Scanner A and across 3 readers for the 324 pairwise comparisons (see Table 18).

**Table 18: Secondary Feature Agreement Rate for Scanner A Across 3 Readers**

		Secondary Feature is Observed Using Iteration j		
		Yes	No	
Secondary Feature is Observed Using Iteration i	Yes	a 	b 	a  +b 
	No	c 	d 	c  +d 
		a  +c 	b  +d 	324

The required overall 2x2 table for a specific secondary feature will be constructed by pooling all 2x2 tables across the 3 reading pathologists and across the 3 scanners, as shown in Table 19.

**Table 19: Overall Secondary Feature Agreement Rate**

		Secondary Feature is Observed Using Iteration j		
		Yes	No	
Secondary Feature is Observed Using Iteration i	Yes	a *	b *	a * +b *
	No	c *	d *	c * +d *
		a * +c *	b * +d *	972

This overall contingency table (Table 19) will be generated for each of the 21 study features (7 features per magnification, 3 magnifications) that appear as a secondary feature and the positive, negative, and overall agreement rates for each secondary feature will be estimated as:

positive agreement	$a^*/972$
negative agreement	$d^*/972$
overall agreement	$(a^*+d^*)/972$

To preserve the correlation structure of multiple readings of the same secondary feature on an FOV, the bootstrap method will be used to derive a two-sided 95% confidence interval (CI) for the overall percent positive agreement. The following data generation mechanism will be followed to preserve the correlation structure in this sub-study.

- Choose 3 scanners **without** replacement.
- For each scanner, choose 36 FOVs **with** replacement from each set assigned to that scanner.
- Identify the reader for each of the selected FOV-scanner combinations.
- For each FOV-scanner-reader combination, calculate the within RP agreement status between reading sessions (1, 2), (1, 3), and (2, 3).
- Estimate the overall intra-scanner percent positive agreement using the sampled data.
- Repeat step a to step e at least 1000 times to estimate a two-sided 95% CI for the percent positive agreement.

Two-sided 95% CI for the negative and overall agreement rates will be estimated concurrently using the same bootstrap. When the estimated agreement rate is at extreme values such as 0% or 100%, the arcsine variance transformation approach, using the Anscombe correction for the continuity, will be used to calculate the 95% confidence interval instead of using the bootstrap.

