Scanner C	a^3+d^3	1134	(a^3+d^3)/1134	
Overall	a^*+d^*	3402	(a^*+d^*)/3402	

The overall Intra-Scanner agreement rate will be calculated by averaging all pairwise comparisons results over all 378 slides with selected study features enrolled and all three pathologists. The overall number is 378 slides with selected features x 3 scanners x 3 readers = 3402. To preserve the correlation structure of multiple readings of the same feature and possibly multiple features on an FOV, the bootstrap method will be used to derive a two-sided 95% CI for the overall agreement rate. An FOV will be the bootstrap re-sampling unit.

Above analyses will be performed for primary feature.

The study acceptance criterion is 85%. The lower limit of the 95% CI for the overall agreement rate will be compared to 85% and if the lower limit is greater than 85%, then the study will have demonstrated intra-scanner precision.

In addition to the overall agreement given in [Table 9](#), overall average positive agreement (APA) and overall average negative agreement (ANA) will be provided with their corresponding two-sided 95% CIs.

In [Table 8](#), the percent agreement of scan i with scan j for a positive result is called positive percent agreement (PPA) and is defined as

$$PPA = a^1/(a^1+c^1)$$

The percent agreement of scan i with scan j for a negative result is called negative percent agreement (NPA) and is defined as

$$NPA = d^1/(b^1+d^1)$$

When obtaining PPA or NPA, one cannot assume either scan i or scan j is the reference. Thus, it is suggested that a reasonable summary of positive agreement between two scans is an average of the two PPAs, and a reasonable summary of negative agreement is an average of the two NPAs. These averages should be weighted to reflect the different marginal totals that are used when scan i or scan j is used as the reference. Clinical and Laboratory Standards Institute (28) defines APA and ANA as follows:

$$APA = 2 a^1/(2a^1+b^1+c^1)$$

$$ANA = 2 d^1/(c^1+b^1+2d^1)$$

Table 10 provides the overall APA and overall ANA rates with corresponding 2-sided, 95% CIs by pooling all pairwise comparisons over the three scanners.

Table 10: Intra-Scanner Overall APA and Overall ANA Rates					
	Number of Pairwise Agreement	APA Agreement Rate		ANA Agreement Rate	
		%	95% CI	%	95% CI
Overall	a^*+d^*	$2a^*/(2a^*+b^*+c^*)$		$2d^*/(c^*+b^*+2d^*)$	

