8.1.3 Statistical Analysis of Secondary Features

The presence of secondary features in the FOVs is expected to be sparse because the FOV is selected for a specific primary feature.

The objective of the analysis is to investigate the frequency distribution of the absence or presence of the secondary features. Each feature will be considered primary for 18 FOVs (3 organs x 6 FOVs per organ) and will be considered secondary for the remaining 360 FOVs (this means n_1 of the 18 FOVs in set 1, n_2 of 18 FOVs in set 2, and n_3 of 18 FOVs in set 3, where $n_1+n_2+n_3=18$). It is possible that a given feature may not be present in the majority of the 360 FOVs.

The secondary analysis will be based on the repeatability/reproducibility regarding each secondary feature separately. To perform the secondary analysis for a specific feature, say feature X, 3 scans (scan1, scan2, and scan3) per scanner will be used. In the 3 scans from scanner A, there are n_1 FOVs primary for feature X among 126 FOVs and $126-n_1$ FOVs secondary for feature X. Thus, $126-n_1$ FOVs will be used to construct the following 2x2 contingency table.

Table 11: Intra Scanner/Inter Scan Secondary Analysis for Scanner A					
		Secondary Feature X is Observed Using Scan2			
		Yes	No		
Secondary Feature X is Observed Using Scan1	Yes	a	b	a+b	
	No	c	d	c+d	
		a+c	b+d	$126-n_1$	

Nine (9) 2x2 tables will be pooled within scanner A and across 3 readers to create [Table 12](#) for scan_i versus scan_j for reader k ($k=1,2,3$) and $i \neq j$ (for $i=1,2,3$ and $j>i$).

Table 12: Intra-Scanner/Inter-Scan Secondary Analysis for Scanner A Across all 3 Readers

		Secondary Feature is Observed Using Scan _i		
		Yes	No	
Secondary Feature is Observed Using Scan _i	Yes	a ¹	b ¹	a ¹ +b ¹
	No	c ¹	d ¹	c ¹ +d ¹
		a ¹ +c ¹	b ¹ +d ¹	1134 – 3(n ₁ +n ₂ +n ₃)

Repeatability and reproducibility of the reading results (i.e., overall APA and overall ANA) will be provided as shown in [Table 13](#) for each of the 21 features that appear as secondary features. In total, up to 21 contingency tables, one for each secondary feature, will be provided, based on the 3240 (3402 – 9 x 18) pairwise comparisons across all 3 readers and all 3 scanners.

Table 13: Overall APA and Overall ANA Rates for Secondary Feature Analysis

	Number of Pairwise Agreement	APA Agreement Rate	ANA Agreement Rate
		%	%
Overall	a [*] +d [*]	2a [*] /(2a [*] +b [*] + c [*])	2d [*] /(c [*] + b [*] +2d [*])

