Reader	Reading Session	Scanner A	Scanner B	Scanner C
1	1	2	3	1
1	2	1	2	3
1	3	3	1	2
2	1	1	2	3
2	2	2	3	1
2	3	3	1	2
3	1	3	1	2
3	2	2	3	1
3	3	1	2	3
Total scans read		1134	1134	1134

[Table 15](#) provides the number of scans pooled over reading sessions.

Table 15: Slides Pooled over Reading Sessions

Reader	Scanner A	Scanner B	Scanner C
1	378	378	378
2	378	378	378
3	378	378	378
Total	1134	1134	1134

To evaluate the Inter-Scanner precision, we need to estimate the precision for three pairwise comparisons, namely scanner A versus scanner B, scanner A vs. scanner C, and scanner B vs. scanner C. For the pairwise comparison, three (3) 2x2 tables similar to [Table 8](#) can be constructed for each of 3 readers and each reading session. Inter-Scanner precision for each reader can be created by pooling the nine (9) 2x2 tables for each reader. In addition, the overall Inter-Scanner precision will be estimated by pooling three 2x2 contingency tables across 3 readers as shown in [Table 16](#).

Table 16: Inter-Scanner Results

	Number of Pairwise Agreement	Number of Comparison Pairs	Agreement Rate	
			%	95% CI
Reader 1	a^1+d^1	1134	$(a^1+d^1)/1134$	
Reader 2	a^2+d^2	1134	$(a^2+d^2)/1134$	
Reader 3	a^3+d^3	1134	$(a^3+d^3)/1134$	
Overall	a^*+d^*	3402	$(a^*+d^*)/3402$	

The two-sided 95% CI for overall Inter-Scanner agreement rate will be calculated in a manner similar to the one provided for the Intra-Scanner substudy.

The above analyses will be performed for the primary feature.

The study acceptance criterion is 85%. The lower limit of the 95% CI for the overall agreement rate will be compared to 85% and if the lower limit is greater than 85%, then the study will have demonstrated inter-scanner precision.

In addition to the overall agreement, overall APA and overall ANA rates for inter-scanner precision will be provided with their corresponding two-sided 95% CIs.

Analysis of secondary features will be similar to the analysis described for the intra-scanner substudy (see section 8.1.3).

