**Figure 1: Example CRF for Feature Detection at 40x Magnification**

### **3.1 Required Number of Slides**

The required number of slides is based upon the previously conducted study for the PIPS system. In all three sub-studies, the precision will be based on three reading pathologists' assessments and identification of specific histologic features that are observed in TIFF images of FOVs containing a primary feature.

In two PowerPoint presentations (19) (20) the FDA has stated that manufacturers seeking clearance of their WSI devices for primary diagnosis in surgical pathology must demonstrate that a pathologist using WSI technology can achieve reproducible detection of histologic features. Those presentations provide only some general guidelines regarding the number of features, organ systems, magnification at which feature is detected, and number of scanners and readers. The additional information from the clearance letter and device summary provides deeper insight into the approval process for which substantial equivalence must be demonstrated.

In the FDA information, three sub-studies for intra-scanner, inter-scanner, and inter-site repeatability and reproducibility are described (21) and further information is also provided related to the number of sites, scanners, pathologists, features, organs, magnifications, and examination of a limited FOV for detection of features. In addition, the precision of feature detection is mentioned as a special control for WSI clearance. (2)

Outside of the FDA released information, further information is available from ClinicalTrials.gov study registration website (22) as well as presentations made by Philips, (23) in May 2017, at the Pathology Informatics Summit in Pittsburgh, PA. (24) Philips presented their features study with the features selected, the different magnifications, multiple choice selections of the expected feature, inclusion and exclusion criteria for slides with the desired feature, the limited FOV used for feature detection, and the acceptance criterion. According to the presentation, the acceptance criterion was established as the lower limit of the 95% confidence interval greater than 85% for overall agreement. Additional discussions with FDA clarified that the acceptance criterion for the current study was the lower limit of the 95% confidence interval for Positive Agreement.

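### The SAP's positive and negative agreement for secondary features are both-yes and both-no shares of all pairs. They replace the protocol's APA and ANA without a stated reason and do not measure repeatability of positive or negative calls.

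*SAP*

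**What the plan says.** Below, a, b, c and d are the pooled cells that the SAP stars in Table 19, and N is the total number of pairs.

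- **Aim.** SAP 6.4.3 sets out to examine repeatability and reproducibility of the readers' "absence or presence calls of the secondary features".
- **Formulas.** Under Table 19 the "positive, negative, and overall agreement rates for each secondary feature will be estimated as" a/972 (positive), d/972 (negative) and (a+d)/972 (overall).
- **Intervals.** A bootstrap interval is planned for the positive rate, and "Two-sided 95% CI for the negative and overall agreement rates will be estimated concurrently using the same bootstrap".
- **Other sub-studies.** SAP 6.5.3 applies the same method between scanners. SAP 6.6.3 applies a similar one between sites, with N = 324.
- **Protocol.** Section 8.1.3 names the measure: "Repeatability and reproducibility of the reading results (i.e., overall APA and overall ANA) will be provided" for each secondary feature (Table 13). Section 8.1.2 cites a laboratory-standards guideline that "defines APA and ANA as follows": APA = 2a/(2a+b+c) and ANA = 2d/(2d+b+c). Its reasoning is that neither scan can serve as the reference. Sections 8.2 and 8.3 carry this over: "Analysis of secondary features will be similar to the analysis described for the intra-scanner substudy".
- **Expected frequency.** Protocol 8.1.3: "The presence of secondary features in the FOVs is expected to be sparse". SAP 6.4.3 likewise allows that a feature may be missing from most of its 108 FOVs.
- **Reason for change.** APA and ANA do not appear in the SAP. The nearest explanation, in SAP 3.1, is that discussions with FDA clarified that the "acceptance criterion for the current study was the lower limit of the 95% confidence interval for Positive Agreement". That concerns the acceptance criterion, and secondary features have none.

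**The concern.** A rate labelled positive agreement should say how often a positive call is repeated. Dividing the both-yes count by all pairs does not do that. If every call is repeated exactly, the SAP's positive rate equals the call frequency. It reaches 100% only if the feature is called in every read. A feature that is never called scores 0%, although all reads agree.

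The form a/N comes from the SAP's primary analysis. There each FOV contains an enrolled feature and a yes means that it was correctly detected, so both-yes can be read as repeated success. In Table 17 a yes means only that the secondary feature was observed. In most FOVs, agreement on absence may be the expected result.

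At stake are the labels of two descriptive rates, the meaning of their two intervals, and consistency between SAP and protocol.

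**Working it through.** **1. The SAP's counts reproduce.** Secondary FOVs per feature: 6 × 3 × 6 = 108, or 36 per set. Per scanner: 36 FOVs × 3 iteration pairs × 3 readers = 324. Over three scanners: 324 × 3 = 972. Inter-site: 36 × 3 × 3 = 324. The protocol's 3402 − 9 × 18 = 3240 also reproduces; its wider base is a separate matter. The problem lies in what is divided by N, not in N.

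**2. Algebra.**
- a/N + d/N = (a+d)/N, the overall agreement. The positive and negative rates therefore cannot both be high.
- Call frequency is (2a+b+c)/(2N) = a/N + (b+c)/(2N). So a/N is bounded above by it, with equality only when b+c = 0.
- With p = a/N and q = d/N, 2a+b+c = N(1+p−q). Hence APA = 2p/(1+p−q) and ANA = 2q/(1+q−p), and both point estimates follow from the reported rates.

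**3. Illustration.** The documents give no call frequencies, so the counts are assumptions. N = 972.

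| Case | a | b+c | d | SAP positive a/N | SAP negative d/N | Overall | APA | ANA | Call frequency |
|---|---|---|---|---|---|---|---|---|---|
| 1 | 45 | 0 | 927 | 4.6% | 95.4% | 100% | 100% | 100% | 4.6% |
| 2 | 45 | 200 | 727 | 4.6% | 74.8% | 79.4% | 31.0% | 87.9% | 14.9% |
| 3 | 20 | 52 | 900 | 2.1% | 92.6% | 94.7% | 43.5% | 97.2% | 4.7% |

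For case 2, APA = 90/(90+200) = 31.0%, ANA = 1454/(1454+200) = 87.9%, and call frequency = 290/1944 = 14.9%. Through the recovery formula, APA = 0.0926/(1+0.0463−0.7479) = 31.0%.

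Cases 1 and 2 have the same SAP positive rate, yet positive calls are repeated perfectly in one and poorly in the other. In case 3, 92.6 of the 94.7 points of overall agreement come from d, so a high overall rate sits beside an APA below one half.

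**4. Intervals, illustrative only.** Case 3 was bootstrapped with 20,000 resamples and its yes calls spread over 10 FOVs. With whole FOVs resampled, the interval is 0.6–3.8% for a/N and 23.5–58.1% for APA. With FOVs drawn separately for each scanner and set, it is 0.9–3.4% and 25.6–58.6%. Two other layouts of the same table, with whole FOVs resampled, gave APA intervals of 37–48% and 11–68%. The widths therefore depend on assumed clustering. What does not depend on it is that the two intervals describe different quantities.

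**The case against.** **Overall agreement is also planned, with an interval.** A reader might infer that none of the planned intervals measures repeatability. The documents do not support that: (a+d)/N is raw repeatability and has its own interval. In case 1 the report would show 100% overall next to 4.6%. This stands, and it limits the point to the positive and negative rates. It does not remove the point, because in case 3 overall agreement is 94.7% while APA is 43.5%.

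**Call frequency is only a bound.** A reader might also infer that a/N simply reports how often the feature is called. Cases 1 and 2 refute this: both give 4.6%, with call frequencies of 4.6% and 14.9%. Equality needs b+c = 0.

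**Nothing promised in the protocol is lost.** Protocol Table 13 has no interval column for secondary features, and the APA and ANA point estimates can be recovered. That is correct. But the SAP chose to add intervals, and those for APA and ANA cannot be derived from intervals for joint proportions.

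**The choice has some logic.** Protocol 8.1.3 also speaks of a frequency distribution of presence and absence, which joint proportions partly serve. They match the SAP's primary-analysis convention and can always be estimated. This supports keeping them under accurate labels. It does not make them the repeatability measure, for which the protocol names APA and ANA.

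**Conclusion.** The point holds as a minor one. In SAP 6.4.3, and by reference 6.5.3 and 6.6.3, the positive and negative rates and their two intervals do not measure repeatability of positive or negative calls. They depart from the protocol's APA and ANA without explanation.

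The algebra needs no assumption. The sizes in the table rest on assumed counts, and the interval widths on assumed clustering as well, so neither predicts this study's results.

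A reader might infer that the study's success decision is at risk. It is not: no acceptance criterion uses the secondary-feature rates, and the 85% comparison is unaffected by this point.

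**What to change.** In SAP 6.4.3, 6.5.3 and 6.6.3:

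- Define positive agreement as APA = 2a/(2a+b+c) and negative agreement as ANA = 2d/(2d+b+c), using the pooled cells, with intervals from the FOV bootstrap already planned.
- Keep (a+d)/N and its interval.
- If a/N and d/N are kept, label them as the both-yes and both-no proportions.
- Report APA or ANA as not estimable when its denominator is zero, and give the number of resamples excluded for that reason.
- If the joint proportions are meant as the measure, state why the SAP departs from the protocol.

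**Cost.** This changes formulas and labels on the same 2x2 tables and the same resamples, with no new data. The downside is wide or non-estimable intervals for very sparse features. If all readers call a feature in only one of 108 FOVs, the share of resamples with no positive call is (35/36)^36 = 36% when whole FOVs are drawn. It is 0.363³ = 4.8% when FOVs are drawn separately for each scanner and set. With two such FOVs the shares are about 13% and 0.2%.
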